#### **7.1.6.4.1 Survival Follow-up**

Once a subject experiences confirmed disease progression or starts a new anti-cancer therapy, the subject moves into the survival follow-up phase. Subjects who experience confirmed disease progression or who start a new anti-cancer therapy, will also move into survival follow-up and should be contacted by telephone annually to assess for survival status until death, withdrawal of consent, or the end of the study, whichever occurs first.

### **7.1.6.5 Second Course Phase (Retreatment Period)**

Subjects who stop pembrolizumab with SD or better may be eligible for up to one year of additional pembrolizumab therapy if they progress after stopping study treatment. This retreatment is termed the Second Course Phase of this study and is only available if the study remains open and the subject meets the following conditions:

- **Either**
  - Stopped initial treatment with pembrolizumab after attaining an investigator-determined confirmed CR according to RECIST 1.1, and
    - Was treated for at least 24 weeks with pembrolizumab before discontinuing therapy

**Product:** Pembrolizumab

**Protocol/Amendment No.:** UVA Breast 48

V04-13-21

- Received at least two treatments with pembrolizumab beyond the date when the initial CR was declared

**OR**

- Had SD, PR or CR and stopped pembrolizumab treatment after 24 months of study therapy for reasons other than disease progression or intolerance

**AND**

- Experienced an investigator-determined confirmed radiographic disease progression after stopping their initial treatment with pembrolizumab
- Did not receive any anti-cancer treatment since the last dose of pembrolizumab
- Meets the safety parameters listed in the inclusion/exclusion criteria

Subjects who restart treatment will be retreated at the same dose and dose interval as when they last received pembrolizumab. Treatment will be administered for up to one additional year.

Visit requirements are outlined in [Section 6.0](#) – Trial Flow Chart.

## 7.2 Assessing and Recording Adverse Events

### 7.2.1 Time Span for Recording Adverse Events

All adverse events that occur after the consent form is signed but before treatment allocation/randomization must be reported by the investigator if they cause the subject to be excluded from the trial, or are the result of a protocol-specified intervention, including but not limited to washout or discontinuation of usual therapy, diet, placebo treatment or a procedure.

From the time of treatment allocation/randomization through 30 days following cessation of treatment, all adverse events must be reported by the investigator. Such events will be recorded at each examination on the Adverse Event case report forms/worksheets. The reporting timeframe for adverse events meeting any serious criteria is described in [Section 7.2.6](#). The investigator will make every attempt to follow all subjects with non-serious adverse events for outcome.

Adverse events will not be collected for subjects during the pre-screening period (for determination of archival tissue status) as long as that subject has not undergone any protocol-specified procedure or intervention. If the subject requires a blood draw, fresh tumor biopsy etc., the subject is first required to provide consent to the main study and AEs will be captured according to guidelines for standard AE reporting.

### 7.2.2 Definitions

**Adverse Event (AE):** An adverse event is defined as any untoward medical occurrence in a patient or clinical investigation subject administered a pharmaceutical product and which does not necessarily have to have a causal relationship with this treatment. An adverse event can therefore be any unfavorable and unintended sign (including an abnormal laboratory finding, for example), symptom, or disease temporally associated with the use of a medicinal product or protocol-specified procedure,

**Product:** Pembrolizumab

**Protocol/Amendment No.:** UVA Breast 48

V04-13-21

whether or not considered related to the medicinal product or protocol-specified procedure. Any worsening (i.e., any clinically significant adverse change in frequency and/or intensity) of a preexisting condition that is temporally associated with the use of the Merck's product, is also an adverse event.

Changes resulting from normal growth and development that do not vary significantly in frequency or severity from expected levels are not to be considered adverse events.

Merck product includes any pharmaceutical product, biological product, device, diagnostic agent or protocol-specified procedure, whether investigational (including placebo or active comparator medication) or marketed, manufactured by, licensed by, provided by or distributed by Merck for human use.

Adverse events may occur during the course of the use of Merck product in clinical trials, or as prescribed in clinical practice, from overdose (whether accidental or intentional), from abuse and from withdrawal.

Progression of the cancer under study is not considered an adverse event.

**Unexpected AE** – Any adverse event not listed in [Section 7.2.9](#).

**Serious AE:** A serious adverse event is any adverse event occurring at any dose during the study that:

- Results in death;
- Is life threatening;
- Results in persistent or significant disability/incapacity;
- Results in or prolongs an existing inpatient hospitalization;
- Is a congenital anomaly/birth defect;
- Is another important medical event

Note: In addition to the above criteria, adverse events meeting either of the below criteria, although not serious per ICH definition, are reportable to the Merck in the same timeframe as SAEs to meet certain local requirements. Therefore, these events are considered serious by Merck for collection purposes

- Is a new cancer (that is not a condition of the study);
- Is associated with an overdose;

**Unanticipated Adverse Device Effect:** An unanticipated adverse device effect (UADE) is any serious adverse event on health or safety or any life-threatening problem or death caused by, or associated with, a device, if that effect, problem, or death was not previously identified in nature, severity, or degree of incidence in the investigational plan or application (including a supplementary plan or application), or any other unanticipated serious problem associated with a device that relates to the rights, safety, or welfare of subjects.

**Device Failure:** A device has failed if it does not perform according to labeling and negatively impacts the treatment while used according to the labeling.

**Device Malfunction:** A device malfunction is an unexpected change to the device that is contradictory to the labeling and may or may not affect device performance.

Device failure and malfunctions- All investigational device failures and malfunctions will be documented on the CRF and reported in the clinical results.

**Product:** Pembrolizumab

**Protocol/Amendment No.:** UVA Breast 48

V04-13-21

**User Error-** User errors that result in the inability to use the device (ex., contamination) should not be reported as a device malfunctions.

**Unanticipated problem** - An unanticipated problem is any event/experience that meets ALL 3 criteria below:

- Is unexpected in terms of nature, severity or frequency given the research procedures that are described in the protocol-related documents AND in the characteristics of the participant population being studied.
- Is related or possibly related to participation in research. This means that there is a reasonable possibility that the incident may have been caused by the procedures involved in the research study.
- The incident suggests that the research placed the participant or others at greater risk of harm than was previously known or recognized OR results in actual harm to the participant or others.

**Protocol Violation-** A protocol violation is defined as any change, deviation, or departure from the study design or procedures of a research project that is NOT approved by the institution's IRB prior to its initiation or implementation, OR deviation from standard operating procedures, Good Clinical Practices (GCPs), federal, state or local regulations. Protocol violations may or may not be under the control of the study team or UVa staff. These protocol violations may be major or minor violations.

**Suspected Adverse Reaction (as defined in 21 CFR 312.32 (a))**- Any adverse event for which there is a reasonable possibility that the drug caused the adverse event. For the purposes of IND safety reporting, "reasonable possibility" means there is evidence to suggest a causal relationship between the drug and the adverse event.

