### 7.2.9 Agent-Specific Expected Adverse Events List

#### 7.2.9.1 Pembrolizumab

Treatment-related adverse reactions are described in Section 7 of the Investigator's Brochure.

**Product:** Pembrolizumab

**Protocol/Amendment No.:** UVA Breast 48

V04-13-21

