### **7.2.9.3 Adverse events expected from biopsies**

#### **Adverse events expected from biopsies (highest grade expected—Grade 2)**

- Bleeding
- Bruising
- Pain
- Lymphedema
- Delayed wound healing
- Scarring
- Numbness
- Gross hematuria and/or dysuria and urinary frequency (prostate biopsies)
- hematochezia (prostate biopsies)
- Infection

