### **7.2.11 Recording and Reporting Adverse Events**

#### **7.2.11.1 Process for Recording Adverse Events**

##### Dose-limiting toxicities (DLTs)

DLTs will be entered into Oncore within 5 calendar days of the study team learning of the event. DLTs that are deemed serious and unexpected will be submitted to the IRB per institutional guidelines (see below).

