**Table 10: UVA IRB-HSR Reporting**

Type of Event	To whom will it be reported:	Time Frame for Reporting	How reported?
Any internal event resulting in death that is deemed DEFINITELY related to (caused by) study participation (Note: An internal event is one that occurs in a subject enrolled in a UVa protocol.)	IRB-HSR	Within 24 hours	IRB Online and phone call www.irb.virginia.edu/
Internal, Serious, Unexpected adverse event.	IRB-HSR	Within 7 calendar days from the time the study team received knowledge of the event.  Timeline includes submission of signed hardcopy of AE form.	IRB Online www.irb.virginia.edu/
For Device Studies: Unanticipated adverse device effects (internal)	IRB-HSR	Within 10 day calendar days of the study team receiving knowledge of the event	IRB Online www.irb.virginia.edu/
Unanticipated Problems that are not adverse events or protocol violations This would include a Data Breach.	IRB-HSR	Within 7 calendar days from the time the study team received knowledge of the event.	Unanticipated Problem report form. http://www.virginia.edu/vprgs/irb/HSR_docs/Forms/Reporting_Requirements-Unanticipated_Problems.doc
Protocol Violations ( The IRB-HSR only requires that MAJOR violation be reported, unless otherwise required by your sponsor, if applicable. )  Or  Enrollment Exceptions	IRB-HSR	Within 7 calendar days from the time the study team received knowledge of the event.	Protocol Violation and Enrollment Exception Reporting Form  http://www.virginia.edu/vprgs/irb/hsr_forms.html

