#### **7.2.11.4 Reporting to the FDA**

The Sponsor-Investigator for the study (the UVA PI or designee) is responsible for providing safety updates to the FDA per the following guidelines. The reporting times refer to the time the study team received knowledge of the event.

FDA Reporting Requirements for Pembrolizumab related adverse events

- Serious and unexpected suspected adverse reactions will be reported to the FDA no later than 15 calendar days after the sponsor determines that the requirements for an IND safety report have been met. The FDA will be notified using an FDA Form 3500a.
- Unexpected fatal or life-threatening suspected adverse reactions will be reported to the FDA no later than 7 calendar days after the Sponsor receives the initial information of the event. The FDA will be notified using an FDA Form 3500a.

Other adverse event information will be sent to the FDA in the IND annual report.

FDA Reporting Requirements for HIFU: Unanticipated adverse device effects (UADE)

- Unanticipated adverse device effects (UADEs) will be reported to the FDA no later than 10 calendar days after the Sponsor-Investigator receives the initial information of the event.

Other adverse event information will be sent to the FDA in the IND annual report.

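### For pembrolizumab-attributed events, expectedness rests on listing alone, so a listed serious reaction that is worse or more frequent than described can miss the expedited IRB and FDA reports

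*Combined protocol and SAP*

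**What the plan says.** Section 7.2.2 defines an unexpected adverse event in one line: "Any adverse event not listed in [Section 7.2.9". Section 7.2.9 has three parts. For pembrolizumab, 7.2.9.1 states: "Treatment-related adverse reactions are described in Section 7 of the Investigator's Brochure". For HIFU, 7.2.9.2 points to the device manual. For biopsies, 7.2.9.3 prints a list under the heading "Adverse events expected from biopsies (highest grade expected—Grade 2".

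Three onward reports depend on the word unexpected:

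- Table 10 sends to the IRB within 7 calendar days any "Internal, Serious, Unexpected adverse event".
- Section 7.2.11.1 provides that "DLTs that are deemed serious and unexpected will be submitted to the IRB per institutional guidelines".
- Section 7.2.11.4 provides, for pembrolizumab, that "Serious and unexpected suspected adverse reactions will be reported to the FDA no later than 15 calendar days". It sets a 7-day limit for unexpected reactions that are fatal or life-threatening, and leaves other events to the IND annual report.

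Section 7.2.2 also contains two related definitions with a wider test. An unanticipated adverse device effect (UADE) qualifies "if that effect, problem, or death was not previously identified in nature, severity, or degree of incidence". The first criterion for an unanticipated problem is that it "Is unexpected in terms of nature, severity or frequency given the research procedures".

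**The concern.** The drug-side definition asks only whether the event is listed. It does not ask whether the event is worse, or more common, than the list describes. The device-effect and unanticipated-problem definitions in the same section ask both.

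This matters because Section 4.4 describes the trial as the first to combine HIFU and pembrolizumab in humans, and the secondary hypothesis in 3.2 is that toxicity will resemble what is known for each modality alone. Evidence against that hypothesis could well be a known pembrolizumab reaction occurring at a higher grade or more often than known. The definition, read as written, labels that event expected.

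DLTs are exposed in the same way. Section 7.2.10 defines a DLT as a drug-related toxicity requiring permanent discontinuation under Table 4, and Table 4 is a table of immune-related events associated with pembrolizumab. If the Brochure names those same reactions (an assumption, since it is not available), most DLTs would be expected by definition and would not reach the IRB by the DLT route.

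**Working it through.** The plan states no figure for this point. The check follows the definition through each reporting trigger and then looks for text that would supply the missing element.

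**Step 1. Is there a severity or frequency element, by source of event?**

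- Pembrolizumab (7.2.9.1): none in the protocol, only a pointer to the Brochure.
- HIFU (7.2.9.2): none in the list, only a pointer to the manual. The UADE definition supplies severity and incidence separately for serious device effects.
- Biopsy (7.2.9.3): yes, a Grade 2 ceiling in the heading of the list.

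**Step 2. What changes for a pembrolizumab-related event that is listed but worse than described?** The Table 9 rows use the possible/probable/definite line. Its sub-headers are partly lost in the extracted text, so the Grade 3 column order is reconstructed.

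| Report | If unexpected | If expected |
|---|---|---|
| IRB, serious event (Table 10) | 7 calendar days | not triggered by this row |
| IRB, serious DLT (7.2.11.1) | submitted | not triggered by this route |
| FDA, serious (7.2.11.4) | 15 calendar days | IND annual report |
| FDA, fatal or life-threatening (7.2.11.4) | 7 calendar days | IND annual report |
| OnCore, Grade 2 (Table 9) | 15 days | 30 days (30 − 15 = 15 later) |
| OnCore, Grade 3, no hospitalization | 7 days | 30 days (30 − 7 = 23 later) |
| OnCore, Grade 3, hospitalized | 7 days | 15 days (15 − 7 = 8 later) |
| OnCore, Grade 4–5, definite | 24 hours | 7 days |
| OnCore, Grade 4–5, possible or probable | 7 days | 7 days (no change) |

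**Step 3. Does other text close the gap for pembrolizumab?**

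- The unanticipated-problem row of Table 10 is limited to problems that are not adverse events, so the wider definition in 7.2.2 does not help here.
- The 24-hour IRB report of a death applies whatever the expectedness, but only if the death is definitely related. Section 7.2.3 reserves that attribution for events where a recurrence has been observed, so the route is narrow.
- Section 7.2.12 is a general commitment to follow applicable law. It does not define the term.

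**Step 4. What does not depend on expectedness?**

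- Serious events go to the sponsor within 24 hours and to the drug supplier within 2 working days (7.2.6).
- All DLTs enter OnCore within 5 calendar days (7.2.11.1).
- The stopping rule in 8.2 counts DLTs regardless of listing.
- The DSMC reviews all adverse events (10.7) and meets monthly (10.8).

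Such events are therefore captured. The steps that can fail are the expedited reports to the IRB and the FDA.

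**The case against.** Four arguments on the other side deserve weight.

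1. **Most of 7.2.9 is better protected than the one-line definition suggests.** A reader might infer that a Grade 4 bleed from a research biopsy, or an unusually severe HIFU injury, also counts as expected. The documents do not support that. The biopsy list carries its own Grade 2 ceiling, and on the natural reading a higher grade is outside what is listed. A serious device effect not previously identified in severity or incidence is a UADE and goes to the FDA and the IRB within 10 calendar days. A reader might also infer that an infection listed for biopsies becomes expected when attributed to pembrolizumab. But 7.2.9 is headed as agent-specific and has separate sub-lists, which points the other way. This objection stands, and it confines the point to pembrolizumab-attributed events.

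2. **The Brochure is unseen.** If its Section 7 describes reactions by grade or frequency, those limits might be read as part of the list. This stands as a limit on certainty. It does not remove the defect, because the definition tests listing and does not say that such limits count.

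3. **The FDA consequence may be milder.** The 15-day clock starts when the sponsor determines that the requirements for an IND safety report are met. Section 7.2.2 ties the term suspected adverse reaction to a federal regulation, and 7.2.12 adds general compliance. A sponsor applying the regulation directly might report anyway. This partly stands. The loss of the FDA reports follows from the protocol's wording but is not established as what would happen. The IRB routes name no such outside test in the protocol's text, although the DLT route does refer to institutional guidelines.

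4. **The safety hypothesis is assessed elsewhere.** Section 8.2 summarises adverse events and DLTs by frequency and magnitude, and the DSMC sees them monthly. This stands. The analysis of toxicity is not impaired.

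**Conclusion.** The point holds for pembrolizumab-attributed events. Under 7.2.2 as written, a listed serious reaction that is more severe or more frequent than described is expected. It misses the 7-day IRB row and the DLT-to-IRB route and, on the protocol's wording, the 7- and 15-day FDA reports. OnCore entry is also later by 8 to 23 days for Grade 2 and 3 events, and moves from 24 hours to 7 days for definitely related Grade 4–5 events.

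This rests on a literal reading of the definition and on the Brochure not supplying limits that would be applied. If the Brochure does give grades and these are honoured, the gap shrinks to frequency and to reactions described without a grade. If it does not, the gap extends to any grade.

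It would go too far to conclude that serious toxicity escapes oversight. The sponsor, the drug supplier and the DSMC are informed irrespective of expectedness, the stopping rule still operates, and definitely related deaths go to the IRB within 24 hours. The weakness is in expedited onward reporting. In a first human combination that is still worth correcting, because it is a stated rule that misclassifies events and not merely a missing detail.

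**What to change.** Replace the definition in 7.2.2 with wording such as: *Unexpected AE: an adverse event not listed in 7.2.9 for the agent or procedure to which it is attributed, or not consistent in nature, severity or frequency with what is described there (including the Grade 2 ceiling in 7.2.9.3).* State that this definition governs Tables 9 and 10, 7.2.11.1 and 7.2.11.4.

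This brings the drug term into line with the two related definitions in 7.2.2. It also makes the biopsy ceiling and the agent-specific reading explicit, where now they must be inferred.

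The cost is one sentence in an amendment and a few more expedited reports. Frequency is the harder element. With at most 15 participants no numerical threshold would be reliable, so it has to rest on investigator judgement.

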### 7.2.3 Attribution Assessment

**Attribution** – The determination of whether an adverse event is related to a medical treatment or procedure. Please refer to Table 7 for additional guidance on evaluation of attribution.

**Definite** – Applies to those adverse events which, the investigator feels are incontrovertibly related to study drug or HIFU procedure. An adverse event may be assigned an attribution of definitely related if or when (must have all of the following):

- It follows a reasonable temporal sequence from administration of the test drug or HIFU procedure.
- It could not be reasonably explained by the known characteristics of the subject's clinical state, environmental or toxic factors, or other modes of therapy administered to the subject.
- It disappears or decreases on cessation or reduction in dose with re-exposure to drug. (Note: This is not to be construed as requiring re-exposure of the subject; however, the group of definitely related can only be used when a recurrence is observed.)
- It follows a known pattern of response to the test drug or HIFU procedure.

**Product:** Pembrolizumab

**Protocol/Amendment No.:** UVA Breast 48

V04-13-21

**Probable** – Applies to those adverse events for which, after careful consideration at the time they are evaluated, are felt with a high degree of certainty to be related to the test drug or HIFU procedure. An adverse event may be considered probably related if or when (must have three of the following):

- It follows a reasonable temporal sequence from administration of the test drug or HIFU procedure.
- It could not be reasonably explained by the known characteristics of the subject's clinical state, environmental or toxic factors, or other modes of therapy administered to the subject.
- It disappears or decreases on cessation or reduction in dose. There are important exceptions when an adverse event does not disappear upon discontinuation of the drug, yet drug-relatedness clearly exists (e.g. bone marrow depression, fixed drug eruptions, tardive dyskinesia).
- It follows a known pattern of response to the test drug or HIFU procedure.

**Possible** – Applies to those adverse events for which, after careful consideration at the time they are evaluated, a connection with the test drug administration or HIFU procedure appears unlikely but cannot be ruled out with certainty. An adverse event may be considered possibly related if or when (must have two of the following):

- It follows a reasonable temporal sequence from administration of the test drug or HIFU procedure.
- It could not readily have been produced by the subject's clinical state, environmental or toxic factors, or other modes of therapy administered to the subject.
- It follows a known pattern of response to the test drug or HIFU procedure.

**Unlikely** – Applies to those adverse events for which, after careful consideration at the time they are evaluated, are judged to be unrelated to the test drug or HIFU procedure. An adverse event may be considered unlikely if or when (must have two of the following):

- It does not follow a reasonable temporal sequence from administration of the test drug or HIFU procedure.
- It could readily have been produced by the subject's clinical state, environmental or toxic factors, or other modes of therapy administered to the subject.
- It does not follow a known pattern of response to the test drug or HIFU procedure.
- It does not reappear or worsen when the drug is re-administered.

**Unrelated** – Applies to those adverse events, which after careful consideration, are clearly and incontrovertibly due to extraneous causes (disease, environment, etc.).

